6.1.6 AEs of Special Interest

An AE of special interest (AESI) is any AE that a regulatory authority has mandated be reported on an expedited basis, regardless of the seriousness, expectedness, or relatedness of the AE to the administration of a UCB product/compound. For rozanolixizumab, the following events require immediate reporting (within 24 hours regardless of seriousness) to UCB:

- Potential Hy's Law, defined as $\geq 3 \times$ upper limit of normal (ULN) alanine aminotransferase (ALT) or aspartate aminotransferase (AST) with coexisting $\geq 2 \times$ ULN total bilirubin in the absence of $\geq 2 \times$ ULN alkaline phosphatase (ALP), with no alternative explanation for the biochemical abnormality, must ALWAYS be reported to UCB as an AE of special interest (ie, without waiting for any additional etiologic investigations to have been concluded). Follow-up information should then be reported if an alternative etiology is identified during investigation and monitoring of the participant.

6.1.7 AEs of Special Monitoring

In addition, **AEs of special monitoring** have been identified.

These include:

- Severe headache

Participants suffering from severe headache are requested to complete the headache questionnaire daily until the headache has been resolved. The results of this questionnaire will be listed.

For participants with severe headache a neurological assessment may be performed at the investigators discretion. In addition a lumbar puncture for CSF collection and a CT scan may be performed. The results of these additional assessments will be listed as well.

- Severe gastrointestinal disturbances (i.e. abdominal pain, diarrhea or vomiting)

Study participants who experience moderate or severe diarrhea will have a stool sample collected and analysed. The results of the stool sampling will be listed.

- Opportunistic infection

The number and percentage of participants who experience AEs of special monitoring and who experience AEs of special interest will be summarized by cohort, treatment group, and method of administration, SOC and PT based on the SS. The A listing will be presented by cohort and treatment group for all AEs of special interest/monitoring. Additionally symptoms and frequency of severe headaches will be listed.

6.1.8 AEs of Focus

The following AEs are defined in the Rozanolixizumab program as AEs of focus (please see Appendix 3 for more details)

- Headaches
- Gastrointestinal Disturbances
- Hypersensitivity Reactions
- Anaphylactic Reactions
- Injection Site Reactions
- Infusion Reactions
- Infections
- Opportunistic Infections
- Reductions in Albumin and Plasma Proteins

- Effects on the Kidney
- Drug Related Hepatic Disorders
- Effect on lipids

AEOFs will be summarized by treatment group to tabulate the following:

- Incidence of each AEOFs by SOC, High Level Group Term (HLGT), HLT and PT
- Incidence of each Serious AEOFs by SOC, High Level Group Term (HLGT), HLT and PT
- Incidence of each AEOFs by relationship, SOC, HLGT, HLT and PT
- Incidence of each AEOFs by maximum intensity, SOC, HLGT, HLT and PT

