In UP0060, [REDACTED]-dose SC administration of rozanolixizumab to healthy Japanese, Chinese, and Caucasian study participants was generally well tolerated with an acceptable safety profile after [REDACTED] SC administration of [REDACTED] doses. Overall, patterns in the incidence of TEAEs observed in Japanese and Chinese study participants were generally comparable to those observed in Caucasian participants. In all study participants, a numerically higher incidence of TEAEs was reported for study participants receiving rozanolixizumab (38 participants [77.6%] reported 115 TEAEs) compared with placebo (10 participants [62.5%] reported 23 TEAEs). Among participants receiving rozanolixizumab, there was a trend towards increased incidence of TEAEs with higher doses (55.6%, 75.0%, and 90.0% of participants in the rozanolixizumab [REDACTED] dose groups, respectively). Three participants (6.1%) reported 4 TEAEs of special monitoring (diarrhea [2 events], abdominal pain [1 event], and vomiting [1 event]) in the [REDACTED] cohort, all of moderate intensity. The [REDACTED] dose was concluded by the investigator to be not well tolerated by 1 Caucasian volunteer who reported moderate headache. Dose-dependent reductions in IgG and IgG subclasses, similar to that observed in UP0018, were seen following administration of rozanolixizumab in all 3 ethnicities. Tetanus- and influenza A virus-specific IgG concentrations over time were similar to total IgG following the administration of rozanolixizumab, generally reaching the lowest levels around Day 10 and returning close to Baseline by Day 57; the geometric mean concentrations for tetanus- and influenza A virus-specific antibodies generally remained at acceptable levels for

protection time in all ethnic and dose groups. Overall, the mean value of albumin remained within the normal range over time, and no clinically relevant changes from Baseline were observed. All injection site reactions observed for rozanolixizumab were self-limiting, short-term, and of mild intensity.

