### Protocol-Required Safety Laboratory Assessments

Laboratory Assessments	Parameters			
Hematology	Platelet Count	RBC Indices:	Coagulation:	WBC Count with
	RBC Count	MCV	INR	Differential:
	Hemoglobin	MCH	prothrombin time	Neutrophils
	Hematocrit	%Reticulocytes	activated partial thromboplastin time fibrinogen	Lymphocytes Monocytes Eosinophils Basophils
Clinical Chemistry a	Blood Urea Nitrogen	Potassium	AST/Serum Glutamic-Oxaloacetic Transaminase	Total Protein
	Creatinine	Sodium	ALT/Serum Glutamic-Pyruvic Transaminase	Lipids
	Glucose (non-fasting)	Corrected calcium	Alkaline phosphatase	Total cholesterol
		Phosphate	Total and direct bilirubin	HDL cholesterol LDL cholesterol HDL/LDL ratio Triglycerides
Routine urinalysis	
 
• Specific gravity
 
• pH, protein, glucose, ketone, urobilinogen, bilirubin, blood, nitrite, and leukocytes by dipstick
 
• Microscopic examination (if blood or protein is abnormal)
 
• albumin:creatinine ratio, total protein, albumin, creatinine, alpha-1 microglobulin, and beta-2 microglobulin
 
			
Stool sampling volume b	
 
• Occult blood, microscopy, culture, and lactoferin
 
			
CSF c	
 
• Cell count, Gram staining, culture, protein, glucose, exploratory biomarkers
 
			
Immunology d	
 
• Complements and cytokines
 
			

Laboratory Assessments	Parameters
Other Screening Tests	
 
● Follicle-stimulating hormone (as needed in women of non-childbearing potential only)
 
● Urine alcohol and drug screen (to include at minimum: amphetamines, barbiturates, cocaine, opiates, cannabinoids and benzodiazepines)
 
● Serum human chorionic gonadotropin pregnancy test (as needed for women of childbearing potential)
 
● Serology (Hepatitis B surface antigen, hepatitis B core antibody [both immunoglobulins G and M], hepatitis C virus antibody, and human immunodeficiency virus 1 and 2 antibody)
 
● Tuberculosis test
 
● Screening for influenza, tetanus, and SARS-CoV-2 vaccinations/antibodies to previous SARS-CoV-2-infection
 
● The results of each test must be entered into the electronic case report form
 

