5.6.3 Additional Safety Assessments

5.6.3.1 Clinical laboratory evaluations

Laboratory data (hematology, clinical chemistry, and urinalysis) and changes from Baseline (if applicable) for numeric variables will be listed by cohort, treatment group and time point. Only abnormal laboratory values will be listed. In case of any abnormal value, all values for the respective subject on this laboratory parameter will be listed.

Any laboratory measurements that are BLQ or above the limit of quantification (ALQ) will be handled as described in [Section 6.1.5.1](#). Values outside the reference range for numeric variables will be flagged in the listings and in addition, will be listed separately for each lab category (hematology, chemistry and urinalysis). The reference ranges will also be reported in the listings.

Laboratory measurements satisfying the marked abnormality criteria (see [Section 6.1.9.1](#)) will be flagged.

Screening tests (as specified in Appendix 2 of the protocol) will be listed in a separate listing.

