5.6.3.1.1 Laboratory values over time

Laboratory variables are grouped according to the laboratory function panel (see Appendix 2 of the protocol). Observed laboratory variables and changes from Baseline will be summarized by descriptive statistics at each time point by cohort, treatment group and method of administration based on SS. In addition, TEMAs for hematology and for clinical chemistry abnormalities will be summarized by treatment group and visit.

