6.1.9.1.2 Chemistry

PARAMETER	UNIT (conventional)	UNIT (standard)	MARKED ABNORMALITY CRITERIA
AST (SGOT)	U/L	U/L	>5.0 x ULN
ALT (SGPT)	U/L	U/L	>5.0 x ULN
ALP (Alkaline Phosphatase)	U/L	U/L	>5.0 x ULN
GGT (Gamma Glutamyl Transferase)	U/L	U/L	>5.0 x ULN
Bilirubin (Total)	mg/dL	umol/L	>3.0 x ULN if Baseline value is normal; >3.0 x Baseline value if Baseline is abnormal
Albumin	g/dL	g/L	<2 g/dL; <20 g/L
Creatinine	mg/dL	umol/L	>3.0 x ULN
Estimate glomerular filtrate rate (eGFR) ¹	mL/min/1.73 m	mL/min/1.73 m	eGFR <29 mL/min/1.73 m
C reactive protein (CRP) ²	mg/L	mg/L	>10mg/L
Calcium	mg/dL	mmol/L	Low: Corrected serum calcium of <7.0 mg/dL; <1.75 mmol/L
			High: Corrected serum calcium of >12.5 mg/dL; >3.1 mmol/L
Immunoglobulin G ³	(g/L)	(g/L)	≤1 g/L
Potassium	mmol/L	mmol/L	Low: <2.5 mmol/L
			High: >6.0 mmol/L
Sodium	mmol/L	mmol/L	Low: <125 mmol/L
			High: >155 mmol/L
Glucose ⁴	mg/dL	mmol/L	Low: <40 mg/dL; <2.2 mmol/L
			High: > 250 mg/dL; >13.9 mmol/L
Total Cholesterol	mg/dL	mmol/L	>400 mg/dL; >10.34 mmol/L
Triglycerides	mg/dL	mmol/L	>500 mg/dL; >5.7 mmol/L

Abbreviations: ALT= alanine aminotransferase; AST = aspartate aminotransferase; dL = deciliter; GGT: gamma-glutamyltransferase; L = liter; mg = milligram; mmol = millimoles; µg = microgram; U = unit; ULN = upper limit of normal

Note: Marked abnormality criteria are defined by Grade 3 or higher events according to the CTCAE, Version 5.0 unless otherwise noted.

¹eGFR is calculated using the Chronic Kidney Disease Epidemiology Collaboration or CKD-EPI formula (https://qxmd.com/calculate/calculator_251/egfr-using-ckd-epi) which is $eGFR = 141 * \min(\text{Scr}/\kappa, 1)^{\alpha} * \max(\text{Scr}/\kappa, 1)^{-1.209} * 0.993^{\text{Age}} * 1.018$ [if female] * 1.159 [if black]; where Scr is serum creatinine (mg/dL), κ is

0.7 for females and 0.9 for males, α is -0.329 for females and -0.411 for males, min indicates the minimum of Scr/κ or 1, and max indicates the maximum of Scr/κ or 1. For derivation from values in standard units (umol/L) the κ values are 61.88 for females and 79.56 for males.

²Includes CRP and High Sensitivity (HS) CRP. Reference for marked abnormality criteria: Nehring, S.M.; Goyal, A.; Patel, B.C. (2020). StatPearls Publishing, web link: <https://www.ncbi.nlm.nih.gov/books/NBK441843/>. A moderate elevation of CRP level per referred reference is used for the marked abnormality criteria for RLZ to ensure a change suggestive of inflammatory process is captured.

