		
[CQ99NAM= 'Opportunistic Infection – Adjudicated']
 
The SPs reviews the context of all of a subject's data (AEs and possibly other) and concludes individually.
 
Indicators of relevant cases may be e.g. repetitive occurrences, conjunction of other events or findings considered relevant.
 
All subjects with a case-by-case PT reported that has been confirmed by the SPs to be an OI will be summarized as such in the stand-alone table, along with all of the events identified in Step 1 of this process.
 
[CQ99NAM= 'Opportunistic Infection – Adjudicated']
 
The timing and frequency of Step 2 should be outlined and agreed to by the study team at the beginning of the study. It is suggested that this process be executed multiple times throughout the course of the study, more frequently in the weeks leading up to database lock, and one final time immediately prior to database lock.
 
Following the initial physician review of case-by-case events, subsequent reviews will be based on the cumulative set of case-by-case events present in the database at each time point of spreadsheet creation.
 
Physician decisions from previous runs should be retained in each subsequent run. The final run of the spreadsheet, with all SP decisions on the full set of case-by-case events, will be archived at the conclusion of the study analysis prepared for agency submission.
	
9	Reductions in albumin and plasma proteins	TEAEs with PT='Blood albumin decreased' or PT='Protein albumin ratio' or LLT='Plasma protein abnormal' or LLT='Proteins serum plasma low'	CSR/ SSD/ IB
10	Effects on the kidney	TEAEs in SMQ= 'Acute renal failure'	CSR/ SSD/ IB
11	Drug related hepatic disorders	TEAEs in	CSR/ SSD/ IB

		SMQ='Drug related hepatic disorders - comprehensive search'	
12	Effect on lipids	TEAEs with PT= 'Blood cholesterol increased' or PT= 'Low density lipoprotein increased' or PT= 'Blood triglycerides increased' or PT= 'Hypercholesterolaemia' or PT= 'Hypertriglyceridaemia' or PT= 'Hyperlipidaemia' or PT= 'Dyslipidaemia' or PT= 'Lipids increased'	CSR/ SSD/IB

For each of above-mentioned AEs of focus following analysis will be done:

Analysis	Table shell
Incidence of AEOF xxx	AE T 02
Incidence of AEOF xxx by Relationship	AE T 04b
Incidence of serious AEOF xxx	AE T 02
Incidence of AEOF xxx by Maximum Intensity	AE T 03A

The following output will only be requested as needed and will not be produced routinely:

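### The SAP plans to assess low serum albumin, but the protocol's required chemistry panel does not include it, so zero counts would mean not measured

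*SAP*

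**What the plan says.** SAP section 6.1.8 names "Reductions in Albumin and Plasma Proteins" as one of 12 adverse events of focus. SAP Appendix 3 (section 6.3, item 9) selects this topic from coded adverse-event terms, beginning "TEAEs with PT='Blood albumin decreased' or PT='Protein albumin ratio' or LLT='Plasma protein abnormal" and ending with a term for low serum or plasma proteins.

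SAP section 6.1.9.1.2 sets a marked-abnormality limit for albumin of below 2 g/dL (below 20 g/L). Section 5.6.3.1 says that "Laboratory measurements satisfying the marked abnormality criteria" will be flagged, and section 5.6.3.1.1 says that "TEMAs for hematology and for clinical chemistry abnormalities will be summarized by treatment group and visit".

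The protocol's required laboratory table (Appendix 2) includes total protein and "Corrected calcium" under clinical chemistry. Serum albumin is not there. Albumin occurs only under routine urinalysis, and footnote l of the schedule of activities also places it in urine.

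On the earlier healthy-participant study UP0060, protocol section 2.2 reports that "the mean value of albumin remained within the normal range over time" and adds that no clinically relevant changes from Baseline were seen.

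**The concern.** The SAP promises an assessment for which the protocol requires no measurement. Protocol section 2 explains why albumin is a natural thing to watch: the receptor that the drug blocks recycles both IgG and albumin, and the drug was designed to spare the albumin part. UP0060 could report on albumin because it had the values. This trial introduces manual push, which section 4.1 expects to run at higher infusion rates than used before, and as written it would give no serum albumin result for either method.

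The practical risk lies in reading the output. A zero count for low albumin looks the same whether nobody was low or nobody was tested.

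**Working it through.** No figure in the plan has to be reproduced. The check sets the two lists side by side.

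1. **SAP chemistry criteria (6.1.9.1.2), 16 parameters:** AST, ALT, ALP, GGT, total bilirubin, albumin, creatinine, eGFR, CRP, calcium, IgG, potassium, sodium, glucose, total cholesterol, triglycerides.

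2. **Protocol chemistry panel (Appendix 2):** blood urea nitrogen, creatinine, non-fasting glucose, potassium, sodium, corrected calcium, phosphate, AST, ALT, ALP, total and direct bilirubin, total protein, and lipids.

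3. **Match.** Eleven of the 16 are in the panel directly. IgG has its own row in the schedule of activities, and eGFR is derived from creatinine. That gives 11 + 2 = 13 with a required source. The other 16 − 13 = 3 have none: albumin, "GGT (Gamma Glutamyl Transferase") and "C reactive protein (CRP"). None of the three appears as a blood test elsewhere in Appendix 2 or in the schedule. Only albumin is also a focus topic.

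4. **Is the gap declared?** SAP section 6.2 records one change from the protocol, about how safety results are grouped, and says that all other analyses follow the protocol. No line says that the albumin criterion does not apply here.

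5. **What the output would show.** By default (SAP section 5.1), percentages use the number of participants in the analysis population and treatment group, not the number tested, and a zero frequency is shown without a percentage. Neither rule tells the reader whether a test was done.

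6. **Can total protein stand in?** Only partly. Total protein is albumin plus globulins, and IgG is a globulin. Exclusion criterion 38 limits Screening IgG to 7 to 16 g/L. Each 10% fall in IgG therefore takes 0.10 × 7 = 0.7 g/L to 0.10 × 16 = 1.6 g/L off total protein with albumin unchanged. A fall in total protein is thus expected from the drug's intended action and cannot by itself be attributed to albumin. The SAP also sets no marked-abnormality limit for total protein.

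**The case against.** The strongest reply is that this is a housekeeping mismatch. The SAP criteria read as programme-wide text: the hematology table carries a note for blinded ITP protocols, and Appendix 3 covers all indications. Section 5.6.3.1.1 groups laboratory variables by the protocol's Appendix 2, so a programmer might never print an albumin row. Where no participant has data, section 5.1 has descriptive summaries show only n=0. The focus topic is drawn from coded events, so its table can be produced. Protocol section 8.2.4 requires clinically significant results from local tests outside the protocol to be recorded. Albumin is named in no objective or endpoint, and section 2.3 does not list its reduction among the anticipated adverse effects.

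Most of this stands, and it keeps the point small. It does not remove the gap. Programme-wide origin explains the mismatch without resolving it. The n=0 rule covers descriptive summaries, not counts of events or of abnormal values. The recording rule helps only if someone chooses to run the test, which Appendix 2 leaves to discretion or local rules.

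Three stronger readings are tempting, and the documents do not support them:

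- **The focus topic has no laboratory data at all.** It also covers plasma-protein terms, which total protein partly informs, and total IgG is sampled repeatedly.
- **Albumin must already be run, because calcium is corrected.** Correction normally uses albumin, but the documents do not say how it is done here or require an albumin value to be reported.
- **The trial overlooks a known albumin hazard.** The UP0060 result and the drug's stated design both point the other way.

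**Conclusion.** The mismatch is real and minor. One SAP laboratory criterion that bears on a focus topic has no scheduled data, and the albumin terms of that topic (1 of 12) could be met only through unscheduled testing. A reader might infer that the safety conclusions for all 32 participants are compromised. They are not: incidence of TEAEs, the PK and PD endpoints and the exploratory endpoints can all be analysed as planned, and the laboratory endpoint under other safety refers to clinical chemistry as a class without naming albumin. What is lost is any basis for saying that albumin was unaffected under either method.

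This rests on reading the Appendix 2 table as complete; nothing in it is marked as redacted. It also assumes that the Laboratory Manual, which is not among the documents, does not add albumin. The GGT and CRP limits are inert: neither feeds the liver-injury criteria in SAP section 5.6.3.1.3 or a focus topic.

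**What to change.** Add serum albumin to the Appendix 2 clinical chemistry list and to the data transfer, at the existing chemistry time points. First ask the local laboratory whether it already runs albumin to correct calcium. If it does, the change is one of reporting; if not, it is one more analyte on draws already scheduled. Protocol Amendment 2 made a change of the same kind when it added phosphate for consistency with related studies.

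If the change is no longer feasible, state in SAP sections 6.1.9.1.2 and 6.2 and in the study report that serum albumin was not assessed. Footnote the focus-event table to say that a zero count for the albumin terms is not evidence of no effect. The cost is wording only.

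Optionally, mark the GGT and CRP limits as not applicable to this study. That changes no result.

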6.1.9 Abnormality Criteria for Laboratory, Vital Sign and Electrocardiogram Parameters

6.1.9.1 Laboratory Assessments Marked Abnormality Criteria

The following criteria will be applied in the determination of marked abnormalities for laboratory assessment values. They are based on Version 5 of the Common Terminology Criteria for Adverse Events (CTCAE) grade 3 or higher criteria unless otherwise noted. If both high and low criteria are shown for a parameter, the criteria should be summarized separately in tabular or graphical data summaries.

6.1.9.1.1 Hematology

PARAMETER	UNIT (conventional)	UNIT (standard)	MARKED ABNORMALITY CRITERIA
Hemoglobin	g/dL	g/L	<8.0 g/dL; <80 g/L
WBC (Leukocytes) ¹	10 ⁹ /L	10 ⁹ /L	Low: <2.0 x 10 ⁹ /L High: >30 x 10 ⁹ /L
Lymphocytes Absolute	10 ⁹ /L	10 ⁹ /L	Low: <0.5 x 10 ⁹ /L High: >20 x 10 ⁹ /L
Neutrophils Absolute	10 ⁹ /L	10 ⁹ /L	<1.0 x 10 ⁹ /L
Platelets ²	10 ⁹ /L	10 ⁹ /L	<50.0 x 10 ⁹ /L

¹WBC (Leukocytes) markedly abnormal high criterion is not based on Version 5 CTCAE Grade 3 or higher criteria. Due to the mechanism of action of RLZ, the safety alert is related to infection risk which would be identified by a lower cut-point than the standard which is related to acute leukemias. A markedly abnormal high cut-point >30 x 10⁹/L is applied to flag leukocytosis (George 2012).

²For blinded ITP protocols, Platelets will not be assessed for TEMA because this parameter will be blinded and is expected to be abnormally low due to the participant population and entry criteria.

6.1.9.1.2 Chemistry

PARAMETER	UNIT (conventional)	UNIT (standard)	MARKED ABNORMALITY CRITERIA
AST (SGOT)	U/L	U/L	>5.0 x ULN
ALT (SGPT)	U/L	U/L	>5.0 x ULN
ALP (Alkaline Phosphatase)	U/L	U/L	>5.0 x ULN
GGT (Gamma Glutamyl Transferase)	U/L	U/L	>5.0 x ULN
Bilirubin (Total)	mg/dL	umol/L	>3.0 x ULN if Baseline value is normal; >3.0 x Baseline value if Baseline is abnormal
Albumin	g/dL	g/L	<2 g/dL; <20 g/L
Creatinine	mg/dL	umol/L	>3.0 x ULN
Estimate glomerular filtrate rate (eGFR) ¹	mL/min/1.73 m	mL/min/1.73 m	eGFR <29 mL/min/1.73 m
C reactive protein (CRP) ²	mg/L	mg/L	>10mg/L
Calcium	mg/dL	mmol/L	Low: Corrected serum calcium of <7.0 mg/dL; <1.75 mmol/L
			High: Corrected serum calcium of >12.5 mg/dL; >3.1 mmol/L
Immunoglobulin G ³	(g/L)	(g/L)	≤1 g/L
Potassium	mmol/L	mmol/L	Low: <2.5 mmol/L
			High: >6.0 mmol/L
Sodium	mmol/L	mmol/L	Low: <125 mmol/L
			High: >155 mmol/L
Glucose ⁴	mg/dL	mmol/L	Low: <40 mg/dL; <2.2 mmol/L
			High: > 250 mg/dL; >13.9 mmol/L
Total Cholesterol	mg/dL	mmol/L	>400 mg/dL; >10.34 mmol/L
Triglycerides	mg/dL	mmol/L	>500 mg/dL; >5.7 mmol/L

Abbreviations: ALT= alanine aminotransferase; AST = aspartate aminotransferase; dL = deciliter; GGT: gamma-glutamyltransferase; L = liter; mg = milligram; mmol = millimoles; µg = microgram; U = unit; ULN = upper limit of normal

Note: Marked abnormality criteria are defined by Grade 3 or higher events according to the CTCAE, Version 5.0 unless otherwise noted.

¹eGFR is calculated using the Chronic Kidney Disease Epidemiology Collaboration or CKD-EPI formula (https://qxmd.com/calculate/calculator_251/egfr-using-ckd-epi) which is $eGFR = 141 * \min(\text{Scr}/\kappa, 1)^{\alpha} * \max(\text{Scr}/\kappa, 1)^{-1.209} * 0.993^{\text{Age}} * 1.018$ [if female] * 1.159 [if black]; where Scr is serum creatinine (mg/dL), κ is

0.7 for females and 0.9 for males, α is -0.329 for females and -0.411 for males, min indicates the minimum of Scr/κ or 1, and max indicates the maximum of Scr/κ or 1. For derivation from values in standard units (umol/L) the κ values are 61.88 for females and 79.56 for males.

²Includes CRP and High Sensitivity (HS) CRP. Reference for marked abnormality criteria: Nehring, S.M.; Goyal, A.; Patel, B.C. (2020). StatPearls Publishing, web link: <https://www.ncbi.nlm.nih.gov/books/NBK441843/>. A moderate elevation of CRP level per referred reference is used for the marked abnormality criteria for RLZ to ensure a change suggestive of inflammatory process is captured.

³Immunoglobulin G criterion based on immunodeficiency literature and noted in RLZ study protocols.

⁴Glucose high criterion defined by Grade 3 and higher events according to CTCAE, Version 4.03, June 14, 2010.

